5.3.2. Estimand

Not applicable.

5.3.3. Analysis Methods

Safety and reactogenicity of Ad26.COV2.S in adult participants

The primary safety and reactogenicity objectives for adult participants of the study will be evaluated with AEs, SAEs, AESIs and MAAEs as detailed in Section 5.6.1 for definitions and analyses methods of adverse events.

Refer to Section 5.7.1 for definitions and analyses methods of immunogenicity endpoints.

Analyses will also be performed by subgroup: gestational age group, participant age group at baseline, and the SARS-CoV-2 serostatus at baseline. Refer to Section 5.7.5 for subgroup definitions.

5.4. Secondary Endpoints Analysis

5.4.1. Definition of Endpoints

Safety and reactogenicity of Ad26.COV2.S booster vaccination in adult participants

- Solicited local and systemic AEs for 7 days after (each) vaccination, or until resolution
- Unsolicited AEs for 28 days after (each) vaccination
- SAEs and AESI throughout the study (from vaccination until end of the study, i.e. at least 12 months after delivery)
- MAAEs until 6 months after the last vaccination

• AEs leading to study discontinuation (from vaccination until end of the study)

Refer to Sections 5.6.1 for more details on adverse events definitions.

Pregnancy Outcomes

Pregnancy outcomes in adult participants (including live term birth, live preterm birth, stillbirth, and abortion). Data are captured in the Delivery History eCRF.

Pregnancy-related AEs

Pregnancy related AEs in adult participants, including gestational diabetes, gestational hypertension, premature rupture of membranes, premature labor, premature uterine contractions, poor or restricted fetal growth, pre-eclampsia, eclampsia, vaginal or intrauterine hemorrhage (non-exhaustive).

The complete list of preferred terms to be included as pregnancy related AEs is provided in Section 6.8. Refer to Sections 5.6.1 for more details on adverse events definitions.

Safety in neonates/infants

- SAEs (including Multisystem Inflammatory Syndrome in Children [MIS-C]) and AESIs in neonates/infants from birth to approximately 12 months of age.
- MAAEs for neonates/infants from birth until 6 months of age.
- AEs in neonates/infants leading to study discontinuation from birth until discontinuation.

Refer to Sections 5.6.1 for more details on adverse events definitions and Section 6.9 for MIS-C.

Neonate/infant Outcomes

Neonate/infant outcomes (including normal neonate, term neonate with (or without) complications, preterm neonate with (or without) complications, neonatal infection, respiratory distress, congenital anomalies, neonatal death, low birth weight, and small for gestational age measured from birth until approximately 12 months of age) (non-exhaustive). Data are captured in the Neonatal Medical History eCRF.

Humoral Immune Response in peripheral blood of adult participants

- Serological response to vaccination as measured by ELISA (S-ELISA; EU/mL]) at all blood collection timepoints.
- Serological response to vaccination as measured by VNA titers, 28 days after the first vaccination.
- Serological response to vaccination measured by binding (S-ELISA and/or equivalent assay) and neutralizing (VNA) antibody titers pre-boost and at selected time points post-booster vaccination.

Antibody levels against SARS-CoV-2 in neonates/infants

- Serological response to vaccination as measured by ELISA (S-ELISA, EU/mL) at birth (i.e., in cord blood) and at approximately 2 months, and 6 months of age.
- Serological response to vaccination as measured by VNA titers at birth (i.e., in cord blood).

5.4.2. Estimand(s)

Not applicable.

5.4.3. Analysis Methods

Safety and reactogenicity of Ad26.COV2.S (incl Pregnancy-related AEs)

The secondary safety and reactogenicity endpoints for adult participants and neonates/infants (separately) of the study will be evaluated with AEs, SAEs, AESIs and MAAEs as detailed in Section 5.6.1 for definitions and analyses methods of adverse events.

Key analyses will also be performed by subgroup: gestational age group, participant age group at baseline, and the SARS-CoV-2 serostatus at baseline. Refer to Section 5.7.5 for subgroup definitions.

Refer to Section 6.8 for Pregnancy-related AEs.

Outcomes

The frequency and percentage of participants (adult participants, and neonates/infants, separately) for whom at least one of the indicated outcomes was reported will be reported. For each separate maternal/fetal and neonatal/infant outcome, the number and percentage of participants who experience at least 1 occurrence of the given outcome will also be tabulated. Denominator for the percentages is the number of participants in the considered population and phase (incidence per 100 participants/phase).

Outcomes will be presented by phase (Post-dose 1, Post-booster, Postpartum Follow-up 1, etc., as applicable), as well as over the entire study and follow-up periods. Outcomes may also be presented by subgroup: gestational age group, participant age at screening, and SARS-CoV-2 serostatus at baseline.

Denominator for the percentages is the number of participants in the considered population and phase (incidence per 100 participants/phase).

Humoral Immune Response in peripheral blood of adult participants

Refer to Section 5.7.1 for definitions and analyses methods of immunogenicity endpoints.

Antibody levels against SARS-CoV-2 in neonates/infants

Refer to Section 5.7.1 for definitions and analyses methods of immunogenicity endpoints.

5.5. Exploratory Endpoints Analysis

5.5.1. Definition of Endpoints

Humoral Immune Response in peripheral blood of adult participants

• Serological response to vaccination as measured by VNA titers at all blood collection timepoints

Antibody levels against SARS-CoV-2 in neonates/infants

• Serological response to vaccination as measured by VNA titers at birth (i.e., in cord blood) and at approximately 2 months, and 6 months of age

Correlation between binding antibody (ELISA) titers and neutralizing antibody (VNA) titers to SARS-CoV-2 of adult participants

• Correlation between ELISA (S-ELISA; EU/mL), or equivalent assay and VNA titers at selected timepoints

Humoral Immune Response in adult participants at the time of delivery

• Serological response to vaccination as measured by ELISA (S-ELISA; EU/mL) and/or equivalent assay using serum samples obtained from peripheral blood and cord blood at the time of delivery

Cellular immune response in peripheral blood of adults in a subset of participants

- Th1 and Th2 immune responses as assessed by:
 - Flow cytometry after SARS-CoV-2 S protein peptide stimulation of peripheral blood mononuclear cells (PBMC) and intracellular cytokine staining (ICS) including cluster of differentiation (CD) markers: CD4+/CD8+, tumor necrosis alpha (TNFα), interferon gamma (IFNγ), interleukin (IL)-2, IL-4, IL-5, IL-13, and/or other T helper cell subset (Th1/Th2) markers. OR
 - Dual or single IFNγ and IL-4 enzyme-lined immunospot (ELISpot) assay after stimulation of PBMCs with SARS-CoV-2 protein peptides

Impact of pre-existing humoral immunity against coronavirus other than SARS-CoV-2 at baseline on Ad26.COV2.S vaccine immunogenicity in adult participants

• Analysis of antibodies binding to coronaviruses other than SARS-CoV-2, or other respiratory viruses by ELISA or equivalent assay

Presence of immunoglobulins against SARS-CoV-2 in colostrum and breast milk in adult participants

• IgA and/or other Ig types against SARS-CoV-2 and/or emerging variants in colostrum and breast milk measured by ELISA or equivalent assay

Humoral immune responses in peripheral blood and cord blood of adult participants induced by Ad26.COV2.S as a 1-dose schedule, and before and after booster vaccination at all or selected blood collection time points

- SARS-CoV-2 neutralization as assessed by SARS-CoV-2 neutralization assays VNA
- Adenovirus neutralization as measured by VNA
- Functional and molecular antibody characterization including Fc-mediated viral clearance, avidity, Fc characteristics, immunoglobulin (Ig) subclass and IgG isotype, antibody glycosylation and assessment of antibody repertoire

- Analysis of antibodies to the spike (S), nucleocapsid (N), and receptor binding domain (RBD) of the SARS-CoV-2 S protein, and surface proteins of other coronaviruses
- Epitope-specificity characterization of antibodies
- Cytokine profiling: analysis of cytokines, chemokines, and other proteins of the innate or adaptive immune response in the serum or plasma
- Passive transfer: analysis of immune mediators correlating with protection against experimental SARS-CoV-2 challenge in a suitable animal model
- Analysis of binding and/or neutralizing antibodies against emerging SARS-CoV-2 variants

Cellular immune responses in peripheral blood of adult participants before and after booster vaccination at selected blood collection time points including after booster vaccination, if feasible

Exploratory analyses may include the following for a subset of participants, if feasible:

- Analysis of gene expression in cells stimulated with SARS-CoV-2 S protein peptides, or in unstimulated cells (ex vivo)
- Analysis of messenger ribonucleic acid (mRNA) expression levels of vaccine-induced biomarkers of immune mediated responses
- Cytokine profiling: Analysis of cytokines, chemokines, and other proteins of the immune response in cells stimulated with SARS-CoV-2 S protein peptides, or in unstimulated cells (ex vivo)
- Epitope-specificity characterization for B and T-cells
- Analysis of the phenotype of antigen-specific T and B cells, assessed by single cell analysis

Humoral immune responses in neonates/infants

- SARS-CoV-2 neutralization as assessed by SARS-CoV-2 neutralization assays VNA
- Adenovirus neutralization as measured by VNA
- Functional and molecular antibody characterization including Fc-mediated viral clearance, avidity, Fc characteristics, immunoglobulin (Ig) subclass and IgG isotype, antibody glycosylation, and assessment of antibody repertoire
- Analysis of antibodies to the spike (S), nucleocapsid (N), and receptor binding domain (RBD) of the SARS-CoV-2 S protein, and surface proteins of other coronaviruses
- Epitope-specificity characterization of antibodies
- Cytokine profiling: analysis of cytokines, chemokines, and other proteins of the innate or adaptive immune response in the serum or plasma
- Passive transfer: analysis of immune mediators correlating with protection against experimental SARS-CoV-2 challenge in a suitable animal model
- Analysis of binding and/or neutralizing antibodies against emerging SARS-CoV-2 variants

Occurrence of symptomatic molecularly confirmed COVID-19 and severity of COVID-19 signs and symptoms in adult participants

- The number of adult participants with molecularly confirmed COVID-19
- Presence and severity of COVID-19 signs and symptoms as measured by the Symptoms of Infection with Coronavirus-19 (SIC)

Assessment of SARS-CoV-2 viral load during a confirmed COVID-19 episode in adult participants

• Analysis of SARS-CoV-2 viral load (via qRT-PCR) in nasal swabs collected during a confirmed COVID-19 episode

Changes in the SARS-CoV-2 genome in adult participants

• Identification of SARS-CoV-2 variants by sequencing of nasal swabs samples (as available)

Occurrence of symptomatic molecularly confirmed COVID-19 and severity of COVID-19 signs and symptoms in neonates/infants

- The number of neonates/infants with molecularly confirmed COVID-19
- Presence and severity of COVID-19 signs and symptoms in neonates/infants as measured by the Pediatric Symptoms of Infection with Coronavirus-19 (PedSIC)

Assessment of SARS-CoV-2 viral load during a confirmed COVID-19 episode in neonates/infants

• Analysis of SARS-CoV-2 viral load (via qRT-PCR) in nasal swabs and/or saliva samples (as available) collected during a confirmed COVID-19 episode

Occurrence of asymptomatic infections with SARS-CoV-2 in adult participants

- The number of adult participants with positive non-S ELISA and/or SARS-CoV-2 immunoglobulin assay that is dependent on the SARS-CoV-2 nucleocapsid (N) protein
- Asymptomatic infection detected by RT-PCR

Occurrence of asymptomatic SARS-CoV-2 infection in neonates/infants

- The number of neonates/infants with positive non-S protein ELISA and/or SARS-CoV-2 immunoglobulin assay (eg, N-protein ELISA)
- Asymptomatic infection detected by RT-PCR

Impact of Ad26.COV2.S vaccine on the incidence of co-infections with SARS-CoV-2 and other respiratory pathogens in adult participants

• Analysis of broad respiratory pathogens panel in the nasal swabs collected during a confirmed COVID-19 episode and in a subset of nasal swab samples from adult participants with a symptomatic infection, up to delivery

Impact of Ad26.COV2.S vaccine on the incidence of co-infections with SARS-CoV-2 and other respiratory pathogens in neonates/infants

• Analysis of broad respiratory pathogens panel in the nasal swabs collected during a confirmed COVID-19 episode and in a subset of nasal swab samples from neonates/infants born to participants who have received Ad26.COV2.S during the study period

Immune response in vaccinated adult participants after natural SARS-CoV-2 infection and other potentially informative biomarkers (e.g., those associated with more severe disease)

- Confirmation of SARS-CoV-2 infection by molecular testing
- SARS-CoV-2 neutralizing titers in serum measured by a VNA
- SARS-CoV-2 binding antibodies measured by ELISA: analysis of antibodies binding to the SARS-CoV-2 S and/or N-protein
- Analysis of gene expression by RNA transcript profiling

Immune response in neonates/infants born to participants who have received Ad26.COV2.S during pregnancy after natural SARS-CoV-2 infection

- Confirmation of SARS-CoV-2 infection by molecular testing
- SARS-CoV-2 neutralizing titers in serum measured by a VNA
- SARS-CoV-2-binding antibodies measured by ELISA: analysis of antibodies binding to the SARS-CoV-2 S and/or N-protein

Further exploration of the impact of vaccination with Ad26.COV2.S on coagulation-related parameters in adult participants

- Hematology assessments of complete blood count with differential, including platelet counts (performed locally at the site)
- Analysis of levels of pro- and anti-coagulation factors in plasma/serum including but not limited to: activated partial thromboplastin time, prothrombin time, fibrinogen, D-dimer levels, Lupus anticoagulant, ant-cardiolipin antibody levels, b-2 glycoprotein, anti-PF4 antibody levels (performed retrospectively at central laboratories on stored samples)

Neurodevelopmental status in neonates/infants

• Summary of developmental outcomes using the Ages & Stages Questionnaire (ASQ3) at 2, 6 and 12 months of age

Changes in the SARS-CoV-2 genome in neonates/infants

• Identification of SARS-CoV-2 variants by sequencing of nasal swabs samples (as available)

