5.7.2. Occurrence of Symptomatic Molecularly Confirmed and Asymptomatic COVID19

An immunologic test for SARS-CoV-2 seroconversion (non-S ELISA and/or SARS-CoV-2 immunoglobulin assay) based on SARS-CoV-2 N-protein, will be performed in adult participants to identify cases of asymptomatic infection. The presence of SARS-CoV-2 infection will be assessed at the study site by molecular testing RT-PCR or molecular test result from any available respiratory tract sample. Asymptomatic infections also include those detected by confirmed molecular tests (either in this study or outside study), in the absence of the relevant symptoms.

Procedures to be performed in the event a participant (adult or infant/neonate) experiences signs or symptoms suggesting possible COVID-19 are detailed in CTP Sections 1.3 and 8.1.2. A sign or symptom is considered as absent or present for a COVID-19 episode if observed in the eCOA or eCRF for the COVID-19 episode, and absent if not.

COVID-19 episodes will not be adjudicated. All data presented corresponding to the COVID-19 episode will be based on the SIC (or PedSIC) as detailed in Section 5.7.3.

The following analyses will use the FAS-A set and will be conducted at the time of the final analysis:

The number and percentage of participants with at least one molecularly confirmed symptomatic or asymptomatic SARS-CoV-2 infection will be tabulated by post vaccination visit and for the entire study period. Similar table will be produced for infants.

The number and percentage of participants who are positive by N serology at different time points will be tabulated.

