5.7.3.2. Analysis of Symptoms of Infection with Coronavirus-19 (SIC)

The number and percentage of participants with at least one SARS-CoV-2 infection will be tabulated by vaccination schedule.

In the group of participants seronegative at baseline, the number and percentage of participants with at least one positive N-ELISA, if available, will be tabulated.

For each participant with COVID-19 infection, a narrative will be prepared based on the visit performed 28 days after the onset of COVID-19 signs and symptoms and other selected information from the clinical database, as available:

- participant ID
- vaccination regimen
- sex, race, ethnicity, age, BMI, dates at which vaccinations were received
- pulse oximetry
- physical examination findings based on the visit performed 28 days after the onset of COVID-19 signs and symptoms
- vital signs including body temperature based on the visit performed 28 days after the onset of COVID-19 signs and symptoms
- Humoral immune responses as collected at the planned time points + those obtained from the blood sample taken on the visits performed 3 and 28 days after the onset of COVID-19 signs and symptoms. This information may be presented graphically.

For the analysis of the SIC (Patient Reported Outcomes, PRO) data, the following considerations apply:

- A COVID-19 infection "episode" is defined as a period starting from the first day on which any symptoms is reported until the last day any symptom is reported, within an interval stating up to 5 days prior to a positive PCR test and finishing up and to 42 days after it
- A symptom (e.g. feeling generally unwell, fatigue, physical weakness, cough, etc.) is assumed to be present on each day the associated Yes/No question is answered "Yes" or the associated severity question has a rating > 0.
- If the PRO was not completed due to the participant being too ill or due to the participant being hospitalized, the symptom will be considered present with maximum severity score. If the PRO was completed due to any other reason, no imputations will be done.

Duration of the episode will be calculated as (the end date of the last symptom in that episode – the start date of the first symptom in that episode) + 1. Duration of each symptom will be calculated as last date of symptom reporting – its first date + 1.

The following analyses will be conducted for confirmed SARS-CoV-2 infection cases:

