5.7.5. Definition of Subgroups

For key safety and immunogenicity analyses (S-ELISA, MSD 4-plex and VNA), results will be analyzed by gestational age group at screening and by SARS-CoV-2 serostatus at baseline. Results will be presented by previous vaccination group like other reports.

Subgroups are defined as shown in Table 6 while the derivation of the SARS-CoV-2 Serostatus at baseline is described in Table 7.

Subgroup analysis will ignore unknown, missing and not reported values, unless otherwise specified.

Subgroup	Definition
(at baseline/screening)	
Age Group	• 18-34 years (≥18y to <35y)
	• 35-45 years (≥35y to ≤45y)
Gestational Age Group	• 16-27 weeks (≥16w to <28w)
	• 28-38 weeks (≥28y to ≤38w)
BMI	• underweight $<18.5 \text{ kg/m}^2$
	• normal $18.5 - <25 \text{ kg/m}^2$
	• overweight and obese $>=25 \text{ kg/m}^2$
Race	• Asian
	Black or African American
	• White
	• Other ('Multiple ^a or 'Native Hawaiian or other Pacific Islander' or
	'American Indian or Alaska Native')
Ethnicity	Hispanic or Latino
	Not Hispanic or Latino
SARS-CoV-2 Serostatus	• Negative
	 Not Negative (excluding missing)

Table 6:	Definition	of Subgroups
		0 1

^a If multiple race categories are indicated, the Race is recorded as 'Multiple'.

Vaccination history	SARS-CoV-2 Serostatus at baseline (by N and/or S serology for vaccine naïve, and by N-serology for previously vaccinated individuals) to assess previous infections	Serostatus result at Baseline
Vaccine naïve (Group 4)	If positive in either Roche Elecsys (N serology) or S-Elisa, or both	Positive
	If negative in both	Negative
	If both are missing	Missing
Other vaccines (and no inactive vaccine) based on S protein	If positive by Roche Elecsys (N serology) only (regardless of the S-ELISA result)	Positive
(Moderna, Pfizer, AstraZeneca, Janssen, Sputnik, Novavax)	If negative by Roche Elecsys (N serology) only (regardless of the S-ELISA result)	Negative
	If Roche Elecsys (N serology) is missing (S- ELISA is not used here)	Missing
Others; depends on vaccine		
Inactivated vaccines (e.g. Sinovac, Sinopharm) or combination of vaccines including at least one inactivated vaccine	Since participant is previously vaccinated with an inactivated vaccine, it is not possible to determine serostatus at baseline	Not evaluable

 Table 7:
 Definition of SARS CoV 2 Serostatus at Baseline

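### The serology limb of the adult asymptomatic-infection endpoint counts any N-positive woman, with no baseline-negative and no symptom-free condition

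*SAP*

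**What the plan says.** The objective in SAP Section 1.1 is the occurrence of asymptomatic infection in women who have received the study vaccine. Its serology endpoint, worded the same way in Sections 1.1 and 5.5.1, is "The number of adult participants with positive non-S ELISA and/or SARS-CoV-2 immunoglobulin assay that is dependent on the SARS-CoV-2 nucleocapsid (N) protein". A second endpoint covers asymptomatic infection found by RT-PCR.

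Section 5.7.2 introduces the serology as "An immunologic test for SARS-CoV-2 seroconversion (non-S ELISA and/or SARS-CoV-2 immunoglobulin assay) based on SARS-CoV-2 N-protein", to be used to identify asymptomatic cases. It then adds: "Asymptomatic infections also include those detected by confirmed molecular tests (either in this study or outside study), in the absence of the relevant symptoms". The planned output, on the FAS-A at the final analysis, is: "The number and percentage of participants who are positive by N serology at different time points will be tabulated".

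Section 5.7.3.2, under the SIC heading, plans a further table: "In the group of participants seronegative at baseline, the number and percentage of participants with at least one positive N-ELISA", if that assay is available.

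Table 7 in Section 5.7.5 provides for women who are N-positive at baseline. For those previously given an S-based vaccine, the positive class is "If positive by Roche Elecsys (N serology) only (regardless of the S-ELISA result"). For recipients of inactivated vaccines it says "Since participant is previously vaccinated with an inactivated vaccine, it is not possible to determine serostatus at baseline" and classes them as not evaluable. Section 1.2 allows such women into Group 3, which takes any prior COVID-19 vaccination not covered by Groups 1 and 2.

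**The concern.** An N-positive result shows past exposure to N protein. It does not date the infection, tell infection from an inactivated vaccine, or say whether there were symptoms. To serve as a measure of asymptomatic infection after vaccination, it needs a negative starting point and a symptom-free interval, and the endpoint has neither.

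At stake is how the result is read. A count headed as asymptomatic infection in vaccinated pregnant women could be taken as the rate of silent infection after Ad26.COV2.S, when an unknown part of it arose before Day 1 or was symptomatic.

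**Working it through.** The SAP states no rate or count for this endpoint, so there is no figure to reproduce. The check has two parts.

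**1. Which conditions each place applies**

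| Place in SAP | Baseline-negative required? | Symptom-free required? | Labelled asymptomatic infection? |
|---|---|---|---|
| 1.1 and 5.5.1, serology endpoint | No | No | Yes |
| 5.7.2, description of the N test | Implied by calling it a seroconversion test; no rule given | No | Yes |
| 5.7.2, infections found by molecular test | Not applicable | Yes | Yes |
| 5.7.2, N-positivity by time point | No | No | No |
| 5.7.3.2, N-ELISA table | Yes | No | No |

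No row marked as asymptomatic infection applies both conditions to serology. Three kinds of women therefore meet the endpoint as worded without a new asymptomatic infection:

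- a woman N-positive from infection before Day 1;
- a Group 3 woman carrying N antibody from an inactivated vaccine;
- a woman with a symptomatic infection during the study who then becomes N-positive.

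**2. How far this can move the figure (illustration)**

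Let p0 be the share N-positive at baseline and i the share of baseline negatives who newly become positive. Both are assumed. The endpoint has no post-baseline condition, so baseline positives count.

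- Endpoint as worded: p0 + (1 − p0) × i
- Rate among baseline negatives: i
- Share of the worded count already positive at baseline: p0 / [p0 + (1 − p0) × i]

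With i = 10%:

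| p0 | Endpoint as worded | On the planned 240 | Rate in baseline negatives | Already positive at baseline |
|---|---|---|---|---|
| 10% | 0.10 + 0.90 × 0.10 = 19% | about 46 | 10% | 0.10/0.19 = 53% |
| 20% | 0.20 + 0.80 × 0.10 = 28% | about 67 | 10% | 0.20/0.28 = 71% |
| 50% | 0.50 + 0.50 × 0.10 = 55% | 132 | 10% | 0.50/0.55 = 91% |

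The worded endpoint is thus 1.9, 2.8 or 5.5 times the rate in baseline negatives. If half of new infections were symptomatic (assumed), the asymptomatic rate in baseline negatives would be 10% × 0.5 = 5%.

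The ordering can change. With p0 = 10% and i = 20%, the endpoint is 0.10 + 0.90 × 0.20 = 28%, and women already positive at baseline are 0.10/0.28 = 36% of the count.

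The 240 is the enrolment target. Section 1.2 says enrolment ceased as of amendment 7, so actual counts may be smaller. The percentages do not depend on N. The formula gives an ever-positive proportion, whereas the 5.7.2 table is by visit.

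**The case against.** The best defence is that most of the pieces are already there. Calling the test one for seroconversion shows that new positivity was intended. The 5.7.2 table can be read as prevalence by visit and the 5.7.3.2 table as new positivity in baseline negatives, two complementary displays. If the latter follows Table 7, inactivated-vaccine recipients fall outside it, because they are not evaluable rather than negative. The endpoint is exploratory and descriptive, and Section 5.7.3.2 leaves detail to the DPS.

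Much of this stands, and it rules out several stronger readings that a reader might infer:

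- *That the SAP holds two conflicting definitions of asymptomatic infection.* It does not. The 5.7.3.2 table restricts a tabulation and does not define the endpoint.
- *That a change of assay will create false new infections.* Table 7 names Roche Elecsys and 5.7.3.2 names N-ELISA, but 5.5.1 and 5.7.2 allow either kind of assay, and nothing says that the assay changes between baseline and follow-up. The risk is conditional.
- *That the endpoint mainly reports pre-study infections.* This depends on rates the SAP does not give; the 36% case above shows that it need not be so.

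What the defence does not supply is the count the objective asks for. The seroconversion intent reaches neither the endpoint nor the 5.7.2 table. A by-visit table does not link a woman's baseline to her later result. The 5.7.3.2 table keeps symptomatic seroconverters, and nothing names it as the report of this endpoint. The DPS is not available to settle it.

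**Conclusion.** The point holds on the wording alone: no rule or table in the SAP yields the number of women with a new, asymptomatic, serologically detected infection after vaccination. The endpoint as written also admits prior infections, inactivated-vaccine antibody and symptomatic seroconverters.

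The size is unknown. Under the assumed 10% new seroconversion and 20% or 50% baseline positivity, the reported figure would be 28% or 55% against 10%, before symptomatic cases are removed. The number of inactivated-vaccine recipients is not given, so their share cannot be estimated.

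The correction should be made, but its reach is limited: the endpoint is exploratory, no hypothesis is tested, and no primary result changes.

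**What to change.** In Sections 5.5.1 and 5.7.2, define serologic asymptomatic infection in adults as all of the following:

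- N-negative at baseline;
- N-positive at a later visit, on the same assay where available;
- in the interval, no COVID-19 symptoms recorded for a COVID-19 episode and no symptomatic confirmed infection.

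Say that the symptom condition applies whether or not a molecular test was positive. Section 5.7.3.2 builds an episode around a positive PCR, so borrowing that definition unchanged would leave symptomatic women without a positive test in the asymptomatic count.

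Use baseline N-negative women as the denominator, and report women with missing or not-evaluable baseline serostatus separately. Tie the 5.7.3.2 table to this definition. Keep the all-women N table in 5.7.2, labelled as seroprevalence by visit.

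The cost is SAP wording, a filter on data already planned for collection, and a smaller denominator.
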